8.1.2 Collection and Reporting Serious Adverse Events

Following the subject's written consent to participate in the study, all SAEs, whether related or not related to study drug, must be collected, including those thought to be associated with protocol-specific procedures. All SAEs must be collected that occur from the time the ICF is signed through the Follow-up Week 8 Visit. The investigator should report any SAE occurring after this time period that is believed to be related to study drug or protocol-specific procedures.

All SAEs should be followed to resolution or stabilization.

An SAE report should be completed for any event where doubt exists regarding its status of seriousness.

If the investigator believes that an SAE is not related to the study drug but is potentially related to the conditions of the study (such as a withdrawal of previous therapy or a complication related to study procedure), the relationship should be specified in the narrative section of the SAE Report.

SAEs, whether related or not related to study drug, overdose (see Section 8.3), potential drug induced liver injury (see Section 8.4) and pregnancies (see Section Error! Reference source not f ound.) must be reported within 24 hours of the Investigator becoming aware of the event. For this study we will be capturing SAEs through electronic data capture (EDC) and on the SAE report.

The Investigator is responsible for submitting all applicable events to the Independent Review Board (IRB) as per the IRB's reporting requirements. Additionally, the Investigator, or designated staff, is responsible for entering the SAE information into the Case Report Form (CRF) and safety reporting system (i.e., event term, start/stop dates, causality, and intensity).

Any serious adverse event must be reported immediately or no later than 24 hours after awareness of the event to Pfizer DSU either via the Pfizer SAE Submission Assistant (PSSA) tool or using the Pfizer CT SAE report, that must be sent by facsimile (fax or eFax), to your country's Pfizer DSU. If only limited information is initially available, follow-up reports are required. If an ongoing SAE changes in its intensity or relationship to study drug or if new information becomes available, a follow-up SAE report should be sent within 24 hours of the Investigator becoming aware of the updated information using the same procedure used for the transmission of the initial SAE and the same event term should be used.

The minimum information required for an initial SAE report is:

- Sender of report (Site number, Investigator name)
- Subject identification (subject number)
- Protocol number
- SAE term (if an SAE is being reported)

8.2 Non-serious Adverse Events

A non-serious adverse event is an AE not classified as serious.

8.2.1 Collection and Reporting of Non-serious Adverse Events

All non-serious AEs must be collected that occur from signing the ICF through the Follow-up Week 8 Visit. Non-serious AEs should be followed until conclusion or stabilization or reported as SAEs if they become serious. Follow-up is also required for non-serious AEs that cause interruption or discontinuation of study drug or those that are present at the end of study treatment.

8.2.2 Laboratory Test Abnormalities

The following laboratory test abnormalities should be captured on the non-serious AE CRF page or SAE Report Form (paper or electronic) as appropriate:

- Any laboratory test result that is clinically significant or meets the definition of an SAE;
- Any laboratory abnormality that required the subject to have the study drug discontinued or interrupted;

Any laboratory abnormality that required the subject to receive specific corrective therapy.

8.3 Overdose

An overdose is defined as the accidental or intentional administration of any dose of a product that is considered both excessive and medically important.

All occurrences of overdose (suspected or confirmed) must be communicated to Pfizer or a specified designee within 24 hours and be fully documented as an SAE. Details of any signs or symptoms and their management should be recorded including details of any treatments administered.

Asymptomatic dosing errors (e.g., accidentally taking 2 tablets in one calendar day) should be reported as deviations.

8.4 Potential Drug Induced Liver Injury (DILI)

Wherever possible, timely confirmation of the initial liver-related laboratory abnormalities should occur prior to the reporting of a potential DILI event. All occurrences of potential DILIs, meeting the defined criteria, must be reported as SAEs as per Section 8.1.2.

Potential drug induced liver injury is defined as:

ALT or AST elevation > 3 times the upper limit of normal (ULN)

AND

Total bilirubin > 2 times ULN, without initial findings of cholestasis (elevated serum alkaline phosphatase)

AND

 No other immediately apparent possible causes of ALT or AST elevation and hyperbilirubinemia, including but not limited to, viral hepatitis, pre-existing chronic or acute liver disease, or the administration of other drug(s) known to be hepatotoxic.

The threshold of laboratory abnormalities for a potential DILI case depends on the subject's individual baseline values and underlying conditions. Subjects who present with the following laboratory abnormalities should be evaluated further as potential DILI (Hy's law) cases to definitively determine the etiology of the abnormal laboratory values:

For subjects with baseline AST **OR** ALT **OR** T bili values above the ULN, the following threshold values are used in the definition mentioned above, as needed, depending on which values are above the ULN at baseline:

- Preexisting AST or ALT baseline values above the normal range: AST or ALT values
 ≥2 times the baseline values AND ≥3 × ULN; or ≥8 × ULN (whichever is smaller).
- Preexisting values of T bili above the normal range: T bili level increased from baseline value by an amount of ≥1 × ULN or if the value reaches ≥3 × ULN (whichever is smaller).

If any potential DILI is identified and meets the criteria above, the Pfizer Medical Monitor (or designee) should immediately be contacted for further instruction and whether the subject must discontinue from the study and appropriate follow up requirements. As with any adverse event, as stated per Section 6.5, the Principal Investigator has the ability and the responsibility to determine whether a subject can safely continue in the study.

Process for abnormal liver function tests: If at any visit after initiation of study drug the AST or ALT is > 3x ULN, the following steps should be taken as soon as the investigator is aware: 1. The subject must be informed of the results and instructed to stop study drug, 2. The subject must be instructed to return to the clinic within 3-5 days for Unscheduled visit for repeat LFT panel and further clinical evaluation and testing as appropriate (with consultation with the Medical Monitor), and 3. The Pfizer Medical Monitor should immediately be contacted. Guidance will be provided to augment management as appropriate.

8.5 Environmental Exposure, Exposure During Pregnancy or Breastfeeding, and Occupational Exposure

Environmental exposure occurs when a person not enrolled in the study as a subject receives unplanned direct contact with or exposure to the study intervention. Such exposure may or may not lead to the occurrence of an AE or SAE. Persons at risk for environmental exposure include healthcare providers, family members, and others who may be exposed. An environmental exposure may include EDP, EDB, and occupational exposure.

Any such exposures to the study intervention under study are reportable to Pfizer Safety within 24 hours of investigator awareness.

8.5.1 Exposure During Pregnancy

If, following the Baseline Visit it is subsequently discovered that a study subject is pregnant or may have been pregnant at the time of the investigational produce exposure, including during at least 6 half-lives after the product administration, the investigational product will be permanently discontinued in an appropriate manner (ie, dose tapering if necessary for subject safety). Protocol-required procedures for the study discontinued and the follow-up must be performed on the subject unless contraindicated by the pregnancy (ie, x-ray studies). Other appropriate pregnancy follow-up procedures should be considered if indicated. The investigator must immediately notify the Pfizer Medical Monitor (or designee) and report the event by either using the CT SAE Report Form or via PSSA tool or by completing an Exposure During Pregnancy (EDP) Supplemental Form following the SAE reporting procedures as described in Section 8.1.2.

Follow-up information regarding the course of the pregnancy, including perinatal and neonatal outcome and, where applicable offspring information must also be reported on an EDP Supplemental Form.

Any pregnancy that occurs in a female partner of a male study subject should be reported to the Pfizer DSU. Information on this pregnancy will be collected on an EDP Supplemental Form, as appropriate.

An EDP occurs if:

- A female subject is found to be pregnant while receiving or after discontinuing study intervention.
- A male subject who is receiving or has discontinued study intervention inseminates a female partner.
- A female nonsubject is found to be pregnant while being exposed or having been exposed to study intervention because of environmental exposure. Below are examples of environmental EDP:
- A female family member or healthcare provider reports that she is pregnant after having been exposed to the study intervention by ingestion or skin contact.
- A male family member or healthcare provider who has been exposed to the study intervention by ingestion or skin contact then inseminates his female partner prior to or around the time of conception.

The investigator must report EDP to Pfizer Safety within 24 hours of the investigator's awareness, irrespective of whether an SAE has occurred. The initial information submitted should include the anticipated date of delivery (see below for information related to termination of pregnancy).

If EDP occurs in a subject/subject's partner, the investigator must report this information to Pfizer Safety using the CT SAE Report Form or via PSSA, regardless of whether an SAE has occurred. Details of the pregnancy will be collected after the start of study intervention and until 66 hours after the last dose.

If EDP occurs in the setting of environmental exposure, the investigator must report information to Pfizer Safety using the CT SAE Report Form or via PSSA. Since the exposure information does not pertain to the subject enrolled in the study, the information is not recorded on a CRF; however, a copy of the completed report is maintained in the investigator site file. Follow-up is conducted to obtain general information on the pregnancy and its outcome for all EDP reports with an unknown outcome. The investigator will follow the pregnancy until completion (or until pregnancy termination) and notify Pfizer Safety of the outcome as a follow-up to the initial report. In the case of a live birth, the structural integrity of the neonate

can be assessed at the time of birth. In the event of a termination, the reason(s) for termination should be specified and, if clinically possible, the structural integrity of the terminated fetus should be assessed by gross visual inspection (unless pre-procedure test findings are conclusive for a congenital anomaly and the findings are reported).

Abnormal pregnancy outcomes are considered SAEs. If the outcome of the pregnancy meets the criteria for an SAE (ie, ectopic pregnancy, spontaneous abortion, intrauterine fetal demise, neonatal death, or congenital anomaly in a live-born baby, a terminated fetus, an intrauterine fetal demise, or a neonatal death), the investigator should follow the procedures for reporting SAEs. Additional information about pregnancy outcomes that are reported to Pfizer Safety as SAEs follows:

- Spontaneous abortion including miscarriage and missed abortion should be reported as an SAE;
- Neonatal deaths that occur within 1 month of birth should be reported, without regard to causality, as SAEs. In addition, infant deaths after 1 month should be reported as SAEs when the investigator assesses the infant death as related or possibly related to exposure to the study intervention.

Additional information regarding the EDP may be requested by the sponsor. Further follow-up of birth outcomes will be handled on a case by case basis (eg, follow-up on preterm infants to identify developmental delays). In the case of paternal exposure, the investigator will provide the subject with the Pregnant Partner Release of Information Form to deliver to his partner. The investigator must document in the source documents that the subject was given the Pregnant Partner Release of Information Form to provide to his partner.

8.5.2 Exposure During Breastfeeding

An EDB occurs if:A female subject is found to be breastfeeding while receiving or after discontinuing study intervention.

A female nonsubject is found to be breastfeeding while being exposed or having been
exposed to study intervention (ie, environmental exposure). An example of
environmental EDB is a female family member or healthcare provider who reports
that she is breastfeeding after having been exposed to the study intervention by
ingestion.

The investigator must report EDB to Pfizer Safety within 24 hours of the investigator's awareness, irrespective of whether an SAE has occurred. The information must be reported using the CT SAE Report Form or via PSSA. When EDB occurs in the setting of environmental exposure, the exposure information does not pertain to the subject enrolled in the study, so the information is not recorded on a CRF. However, a copy of the completed report is maintained in the investigator site file.

An EDB report is not created when a Pfizer drug specifically approved for use in breastfeeding women (eg, vitamins) is administered in accordance with authorized use. However, if the infant experiences an SAE associated with such a drug, the SAE is reported together with the EDB.

8.5.3 Occupational Exposure

The investigator must report any instance of occupational exposure to Pfizer Safety within 24 hours of the investigator's awareness using the CT SAE Report Form or via PSSA, regardless of whether there is an associated SAE. Since the information about the occupational exposure does not pertain to a subject enrolled in the study, the information is not recorded on a CRF; however, a copy of the completed report is maintained in the investigator site file.

8.6 Lack of Efficacy

The investigator must report signs, symptoms, and/or clinical sequelae resulting from lack of efficacy. Lack of efficacy or failure of expected pharmacological action is reportable to Pfizer Safety only if associated with an SAE.

8.7 Medication Errors

Medication errors may result from the administration or consumption of the study intervention by the wrong subject, or at the wrong time, or at the wrong dosage strength.

Medication errors are recorded and reported as follows:

Recorded on the Medication Error Page of the CRF	Recorded on the Adverse Event Page of the CRF	Reported on the CT SAE Report Form or PSSA to Pfizer Safety Within 24 Hours of Awareness
All (regardless of whether associated with an AE)	Any AE or SAE associated with the medication error	Only if associated with an SAE

8.8 Adverse Events of Special Interest

Not applicable for this study.

9 STATISTICS

Complete details on the statistical methods for this study may be found the Statistical Analysis Plan (SAP).

9.1 Sample Size

The study will randomize approximately 220 subjects with confirmed episodic migraine per treatment group. Based on data from study BHV3000-305, we estimate that this will result in roughly 200 subjects per treatment group in the migraine analysis set. Assuming rimegepant provides roughly a 1.1 day advantage over placebo on the primary endpoint, and assuming a common standard deviation of 3.5 days, then the study will have roughly 80% power on the primary endpoint at a 2-sided alpha level of 0.025.

In study BHV3000-305, rimegepant provided a 0.8 day advantage over placebo. With daily dosing, we expect the treatment effect to increase. Using the data from study BHV3000-305, the standard deviation of the primary endpoint was estimated to be roughly 3.5 days.

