The study will recruit male and female subjects, 18 years of age or older with at least a one-year history of episodic migraine (with or without aura) consistent with a diagnosis according to the International Classification of Headache Disorders, 3rd edition 4 Per their own report, subjects must have migraine onset prior to age 50, migraine attacks that last 4-72 hours (if not treated), and have had 4-14 migraine attacks per 4 week period within the 12 weeks prior to the Screening Visit. Subjects must also have at least 4 Migraine Days and no more than 14 Headache Days during 28 days in the Observation Phase.

WOCBP who are unwilling or unable to use an acceptable contraceptive method or abstinence to avoid pregnancy for the entire study and for 60 days after the last dose of study drug, women who are pregnant or breastfeeding, and women with a positive pregnancy test at screening or prior to study drug administration will be excluded.

Use of prophylactic migraine medication within 30 days prior to the Screening Visit is prohibited. Subjects with a history of use of analgesics (e.g., non-steroidal anti-inflammatory drugs [NSAIDs] or acetaminophen) or use of medication accepted for treatment of acute migraine for a nonmigraine indication on ≥ 15 days per month during the 3 months (12 weeks) prior to the Screening Visit are excluded. Subjects who previously discontinued biologic migraine medications (such as CGRP monoclonal antibodies) must have done so at least 6 months (24 weeks) prior to the Screening Visit.

Statistical Methods:

The study will randomize approximately 220 subjects with confirmed episodic migraine per treatment group. Based on data from study BHV3000-305, we estimate that this will result in roughly 200 subjects per treatment group in the migraine analysis set. Assuming rimegepant provides roughly a 1.1 day advantage over placebo on the primary endpoint, and assuming a common standard deviation of 3.5 days, then the study will have roughly 80% power on the primary endpoint at a 2-sided alpha level of 0.025.

The primary endpoint, mean change from the Observation Phase in the number of migraine days per month over the entire Double-blind Treatment Phase (Weeks 1 to 12), will be assessed using a linear mixed effects model with repeated measures.

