1.3 Product Development Background

Details of the clinical and preclinical studies are provided in the most current Investigator Brochure. A summary of the relevant data to the study are presented below. Rimegepant is

approved for the treatment of acute treatment and prevention of episodic migraine in the US, UK and EU and is well tolerated in humans when given as single oral dose of 75 mg to treat acute migraine and at a dose of 75 mg EOD for the prevention of episodic migraine. Every other day dosing was well tolerated with no signals of hypersensitivity, cardiovascular events, or hepatotoxicity.²

Rimegepant has been studied up to the maximum dose of 1500 mg and multiple oral doses up to the maximum daily dose of 600 mg for 14 days.

The BHV3000-201 study is a completed Phase 2/3, 52-week, open-label, safety study in 1800 subjects (up to one year in duration) with rimegepant 75 mg dosed as needed or scheduled EOD plus as needed. Rimegepant 75 mg administered in multiple doses for up to 52 weeks in subjects with migraine was well tolerated. No clinically relevant trends in laboratory abnormalities were observed on-treatment or during follow-up.

The BHV3000-305 study is a completed Phase 2/3, 64-week (12 weeks of a double-blind, placebo-controlled phase followed by 52 weeks of open-label treatment) study with rimegepant 75 mg or matching placebo dosed every other day (EOD) for the prevention of migraine. During the open-label phase, subjects were able to dose on non-scheduled dosing days and therefore were able to dose up to once daily.

The primary identified adverse event (AE) of interest is the potential elevation of liver function tests. Investigators must carefully monitor routine liver function tests (alanine aminotransferase [ALT], aspartate aminotransferase [AST], total bilirubin, and ALP) and potentially liver related symptoms and signs. Clinicians should also monitor changes in hematology and other laboratory measures.

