1.4 Benefit Risk Assessment

Rimegepant is approved in the US, EU, and UK for the treatment of migraine in adults, including both acute treatment of migraine and preventive treatment of episodic migraine. Rimegepant appears to be generally safe and well tolerated in humans when given as single oral doses from 75 mg up to the maximum dose of 1,500 mg and multiple oral doses up to the maximum daily dose of 600 mg for 14 days. Rimegepant 75 mg represents an advancement in migraine therapeutics, providing the first CGRP antagonist to demonstrate benefit for both the acute treatment and prophylaxis of migraine. Dual action therapy for migraine with a single agent offers patients the potential for significant clinical advantages including: 1) a simplified medication regimen to treat migraine across the spectrum from acute episodes to the prevention of future attacks, which are 2 manifestations of the same condition; 2) avoiding polypharmacy with concurrent use of multiple medications each with their own side effects; 3) reducing the risk of drug-drug interactions; and 4) cost-effectiveness of a single medication that provides both acute and preventive therapy.

Broad and sustained efficacy of rimegepant 75 mg was demonstrated in 3 previously completed Phase 3 studies (BHV3000-301, BHV3000-302 and BHV3000-303). Statistically significant efficacy was demonstrated on the co-primary endpoints of freedom from pain, and freedom from

most bothersome symptom at 2 hours post-dose. Also, in all 3 studies, significant results were achieved on photophobia freedom, phonophobia freedom and pain relief at 2 hours post-dose. Similar results were demonstrated in the BHV3000-310 study recently completed in China and Korea. In the Phase 2/3 placebo-controlled study (BHV3000-305) for the preventive treatment of migraine, rimegepant at a dose of 75 mg every other day (EOD) demonstrated statistically significant superiority to placebo on the primary endpoint of change from the observation period in the mean number of migraine days per month on treatment in the last month of the double-blind treatment phase.

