1.6 Research Hypothesis

Rimegepant 75 mg ODT is effective and well tolerated when taken daily for the prevention of episodic migraine.

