2.1 Primary

To evaluate the efficacy of EOD and daily rimegepant dosing regimens relative to placebo as a preventive treatment for episodic migraine, as measured by the mean reduction from the Observation Phase in the number of migraine days per month over the entire Double-blind Treatment Phase.

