9.3.1.3 Multiplicity Correction

Type 1 error is controlled by splitting the alpha level between the 2 rimegepant treatment groups and the use of hierarchical testing. The significance of the primary endpoint for each treatment group is evaluated at a 2-sided alpha level of 0.025. If the primary endpoint is significant for a treatment group, then the secondary efficacy and outcomes research endpoints for that treatment group will be tested hierarchically, each at a 2-sided alpha level of 0.025, in the following order:

- Proportion of subjects with ≥ 50% reduction from the Observation Phase in the number of moderate to severe migraine days per month over the entire Double-blind Treatment Phase (Weeks 1 to 12).
- Mean change from the Observation Phase in the number of migraine days per month in the last 4 weeks (Weeks 9 to 12) of the Double-blind Treatment Phase.
- Mean change from the Observation Phase in the number of migraine days per month in the first 4 weeks (Weeks 1 to 4) of the Double-blind Treatment Phase.
- Mean number of acute migraine-specific medication days per month over the entire Doubleblind Treatment Phase (Weeks 1 to 12). Acute migraine-specific medications are triptans and ergotamine.
- Mean change from baseline in the MSQ restrictive role function domain score at Week 12 of the Double-blind Treatment Phase.

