5 SAMPLE SIZE, POWER, AND TYPE 1 ERROR

The study randomizes approximately 220 subjects per arm. Based on data from study C4951025 (BHV3000-305), we estimate that this results in roughly 200 subjects per arm in the migraine analysis set. Assuming rimegepant provides roughly a 1.1-day advantage over placebo on the primary endpoint, a common standard deviation (SD) of 3.5 days, and a 2-sided alpha level of 0.025, then the study has roughly 80% power on the primary endpoint.

In study C4951025 (BHV3000-305), rimegepant provided a 0.8-day advantage over placebo. With daily dosing, we expect the treatment effect to increase. Using the data from study BHV3000-305, the SD of the primary endpoint was estimated to be roughly 3.5 days.

Type 1 error is controlled using a 2-sided alpha level of 0.025 and hierarchical testing. The significance of the primary endpoint is evaluated at a 2-sided alpha level of 0.025 for each rimegepant dosing regimen versus placebo. If the primary endpoint is significant for a rimegepant dosing regimen, then the secondary efficacy and outcomes research endpoints are tested hierarchically, each at a 2-sided alpha level of 0.025, in the order specified in Section

3.2.2. Thus, for a rimegepant dosing regimen, a secondary efficacy or outcomes research endpoint is tested only if the preceding secondary endpoint in the hierarchy is determined to be significant (i.e., p-value ≤ 0.025). If a test in the hierarchy is not significant, then any further tests on endpoints in the sequence have p-values presented only for descriptive purposes, and no conclusions are drawn from those results. Note that secondary safety endpoints are not tested.

For exploratory endpoints, no attempt is made to adjust for multiplicity. Any exploratory endpoints for which p-values are produced are evaluated at an unadjusted, 2-sided alpha level of 0.025 and presented only for descriptive purposes.

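### The roughly 80% power is stated for both primary comparisons but justified only for daily dosing; at the 0.8 day cited from the earlier study, EOD power is about 52%

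*Protocol*

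**What the plan says.** The Synopsis (Statistical Methods), Protocol 9.1 and SAP 5 share the same sample size assumptions: about 220 subjects randomized per group, about 200 of them in the migraine analysis set, a 1.1-day advantage over placebo and a common SD of 3.5 days. The Synopsis and Protocol 9.1 conclude that "the study will have roughly 80% power on the primary endpoint at a 2-sided alpha level of 0.025", and the SAP that "the study has roughly 80% power on the primary endpoint". None of the three names a regimen.

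Protocol 9.1 then gives the basis for the effect, and SAP 5 repeats it: "In study BHV3000-305, rimegepant provided a 0.8 day advantage over placebo. With daily dosing, we expect the treatment effect to increase". The Synopsis gives no basis.

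The primary endpoint carries two tests. Protocol 2.1 states the objective: "To evaluate the efficacy of EOD and daily rimegepant dosing regimens relative to placebo as a preventive treatment for episodic migraine". Protocol 9.3.1.3 adds: "The significance of the primary endpoint for each treatment group is evaluated at a 2-sided alpha level of 0.025". Under that section and SAP 5, the secondary endpoints of a regimen are tested only after its own primary test succeeds.

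Three other places bear on the point:
- Protocol 1.6, the research hypothesis, covers daily dosing only: "Rimegepant 75 mg ODT is effective and well tolerated when taken daily for the prevention of episodic migraine".
- Protocol 1.3 describes BHV3000-305 as comparing rimegepant 75 mg with "matching placebo dosed every other day (EOD) for the prevention of migraine".
- Protocol 1.4 gives that study's primary endpoint as the change in the "mean number of migraine days per month on treatment in the last month of the double-blind treatment phase". In this trial the primary endpoint covers Weeks 1 to 12 (Protocol 3.1).

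**The concern.** The alpha in the power statement, 0.025, is the alpha of each regimen-versus-placebo test. Read with the primary objective, the 80% therefore looks like the power of each of the two primary tests.

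The reason for assuming more than 0.8 day applies to only one of them. The EOD arm alternates active drug with placebo, so its active schedule is the one that produced the 0.8 day in BHV3000-305. No reason is given for expecting 1.1 days from that schedule, and no separate EOD effect or EOD power appears in either document.

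What is at stake is how the EOD result is planned for and read. A non-significant EOD result would be judged against a claimed 80%, although on the documents' own EOD figure the chance of success was about one in two. Because the EOD secondary endpoints can be claimed only if the EOD primary test succeeds, that chance is also an upper limit on claiming any of them.

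**Working it through.** **Inputs**
- Analysed subjects per group n = 200, SD = 3.5 days, effect d = 1.1 days, 2-sided alpha 0.025: Synopsis, Protocol 9.1, SAP 5.
- The same alpha applies to each regimen: Protocol 9.3.1.3, SAP 5.
- Earlier EOD effect 0.8 day: Protocol 9.1, with the regimen from Protocol 1.3.

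**Formulas** (two means, normal approximation)
- SE = SD × √(2/n) = 3.5 × √(2/200) = 0.35 day.
- Critical value z(0.9875) = 2.2414, so the smallest significant difference is 2.2414 × 0.35 = 0.78 day.
- Power = Φ(d/SE − 2.2414).

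**The plan's own figure.** d/SE = 1.1/0.35 = 3.143, and Φ(3.143 − 2.241) = Φ(0.901) = 81.6%. The noncentral t distribution with 398 df gives 81.4%. The sample size for 80% power at 1.1 days is 193 per group. The stated figure reproduces.

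**The same formula at other effects**

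| True effect (days) | d/SE | Power |
|---|---|---|
| 0.7 | 2.000 | 40% |
| 0.8 | 2.286 | 52% |
| 0.9 | 2.571 | 63% |
| 1.0 | 2.857 | 73% |
| 1.1 | 3.143 | 82% |

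At 0.8 day the noncentral t gives 51.5%. If 0.8 was rounded from somewhere between 0.75 and 0.85, power lies between 46% and 57%.

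**Sensitivity at 0.8 day**
- All 220 per group analysed: 56%.
- SD 3.0: 66%. SD 4.0: 40%. This SD range is an assumption.

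**What 80% would need for EOD** (z(0.80) = 0.8416; 2.2414 + 0.8416 = 3.083)
- Effect: 3.083 × 0.35 = 1.08 days, or 1.03 days with 220 analysed.
- SD at 0.8 day and n = 200: 0.8/(3.083 × 0.1) = 2.6 days.
- Group size at 0.8 day: 2 × 3.5² × 3.083²/0.8² = 364 analysed, against 200 planned.

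**Both tests together.** With equal groups and a shared placebo arm the two test statistics have correlation 0.5. If both effects are 1.1 days, the chance of two significant results is 71% and of at least one 92%. If EOD is 0.8 and daily 1.1, these fall to 48% and 86%.

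**The case against.** **The statement is conditional and true.** It says what the power is if the advantage is 1.1 days, and that holds for any regimen with that effect. The 0.8 day and the daily-dosing reason stand next to it in Protocol 9.1 and SAP 5. This is fair: the defect is one of scope, not of calculation. It does not settle the matter, because the text attaches the figure to a primary endpoint that is two tests and says nothing about EOD power.

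**The trial may have been sized on daily dosing by design.** The research hypothesis names only daily dosing. Protocol 1.5 speaks of further evaluating EOD, and Protocol 1.5.2 treats EOD efficacy as already shown. That may well be the intent, but neither document says so, and EOD has its own share of alpha and its own hierarchy.

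**All subjects take a tablet daily, so the daily-dosing reason might cover both arms.** It cannot. Half of the EOD arm's tablets are placebo, and its active schedule matches BHV3000-305.

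**The 0.8 day may not transfer.** The earlier primary endpoint was the last month, the endpoint here is Weeks 1 to 12, and the documents do not say which window the 0.8 day or the SD of 3.5 comes from. This stands. It makes 52% a benchmark rather than the EOD power, and it is why a range is shown.

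**The planned model may be more precise than a two-sample formula.** It adjusts for Observation Phase migraine days and stratum, and the documents do not say whether 3.5 is already an adjusted SD. If it is raw, and the covariates are assumed to explain 10%, 20% or 30% of the variance, power at 0.8 day becomes 57%, 62% or 69%. This stands as a caveat, but it does not reach 80% in that range. It would also raise the stated 80%, which comes from the same unadjusted formula.

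**Conclusion.** The concern holds. The roughly 80% is correct for a 1.1-day effect with 200 analysed per group, SD 3.5 and 2-sided alpha 0.025, and the plan supports that effect for daily dosing only. For EOD the plan gives neither an effect nor a power. At the one EOD effect it cites, 0.8 day, power is about 52%, some 30 points below the 82% at 1.1 days. It stays under 80% for any EOD effect below 1.08 days.

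The 52% assumes that 0.8 day applies to Weeks 1 to 12 in this trial and that 3.5 days is the SD relevant to the analysis. Neither is stated. The gap narrows under more favourable assumptions but does not close in the ranges examined.

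Type I error control, the power of the daily comparison at its stated effect, and the validity of both treatment estimates are unaffected. This should be corrected because the figure is relied on for one of two primary comparisons, but it is a correction to what is stated, not to the design.

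**What to change.** In the Synopsis, Protocol 9.1 and SAP 5, state the power by comparison. For example:

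> With about 200 analysed subjects per group, an SD of 3.5 days and 2-sided alpha 0.025, power is about 80% for rimegepant daily versus placebo if the true difference is 1.1 days. For rimegepant EOD versus placebo, power is about 52% if the true difference is 0.8 day, 63% if it is 0.9 and 73% if it is 1.0.

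The sponsor may substitute its own EOD assumption, provided the assumption and its power are written down. Alternatively, keep one figure and give a reason for expecting 1.1 days with EOD.

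In the same place, say whether the 0.8 day refers to the last month or to Weeks 1 to 12. It would help to say the same of the SD, and whether it is raw or model-based.

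The cost is wording in three places, and a less favourable stated figure for one of the two comparisons. Enrolment, alpha and analysis do not change.
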